26.2.1. Required Documentation	
26.2.1. Procedure for initiating/opening a new site	40
26.2.3. Principal Investigator Responsibilities	40
26.3. APPENDIX 3 - PROTOCOL AND AMENDMENT HISTO	ORY41
26.4. Safety Reporting Flow Chart	48

3. Abbreviations

AE/AR	Adverse event/Adverse Reaction
CA	Competent Authority
ССТИ	Cambridge Clinical Trials Unit
CRF	Case Report Form
CTIMP	Clinical Trial of Investigational Medicinal Product
UCam	University of Cambridge
DSUR	Development Safety Update Report
GCP	Good Clinical Practice
ICF	Informed Consent Form
IMP	Investigational Medicinal Product
MDA	Mass Drug Administration
NHS	National Health Service
NTD	Neglected Tropical Disease
PIS	Participant Information Sheet
PZQ	Praziquantel
R&D	Research and Development
RA	Regulatory Agency
REC	Research Ethics Committee
SAE/SAR	Serious Adverse Event/Serious Adverse Reaction
SCORE	Schistosomiasis Consortium for Operational Research and Evaluation
SUSAR	Suspected Unexpected Serious Adverse Reaction
TMG	Trial Management Group
TSC	Trial Steering Committee
VCD	Vector Control Division

[figure not shown]
4. Trial Synopsis

Title of clinical trial	Impact of increased praziquantel frequency on childhood fibrosis in persistent schistosomiasis morbidity hotspots. A phase IV CTIMP trial.
Sponsor name	Cambridge University Hospitals NHS Foundation Trust and University of Cambridge
ISRCTN Number	16994599
Medical condition or disease under investigation	Periportal fibrosis of the liver caused by schistosomiasis mansoni
Purpose of clinical trial	To ascertain the most effective treat- ment frequency for morbidity control
Primary objective	To compare the effect of 2x and 4x treatments annually with praziquantel to the standard 1x annual treatment on the prevalence of Schistosoma mansoni associated periportal fibrosis of the liver.
Secondary objective (s)	To compare the effect of 2x and 4x treatments annually with praziquantel to the standard 1x annual treatment on the mean infection intensity of Schistosoma mansoni.
Trial Design	Phase IV, single centre, randomised, trial, single blinded to the primary outcome assessors, but open label to all other investigators and participants.
Trial Outcome Measures	Ultrasound periportal fibrosis pattern scores.
Sample Size	600

Summary of eligibility criteria	 Inclusion Criteria: Aged 6-14yrs Resident in study village for at least 2years Parental/Guardian consent granted Child assent granted Exclusion Criteria Previous facial oedema after praziquantel treatment Known neurocysticercosis or ocular cysticercosis
Investigational medicinal product and dosage	Praziquantel, ~40mg/kg according to standardised WHO dose pole.
Active comparator product(s)	Standard annual treatment with pra- ziquantel
NIMPs and Challenge Agents	_
Route(s) of administration	Oral
Maximum duration of treat- ment of a participant	One oral dose per treatment round
Procedures: Screening & enrolment	Demographic data - age, sex, length of residency, history of severe praziquantel side effects
Procedures: Baseline	Ultrasonography - WHO Niamey Proto- col Faecal parasite egg counts Urine samples Blood sample
Procedures: Treatment period	Control arm – PZQ treatment annually Intervention arm 1 – treatment with PZQ twice annually Intervention arm 2 – treatment with PZQ 4 times annually
	Treatment schedule based around Ugandan school terms, at approximate but not exactly equal intervals.
	At time of 1-year treatment of all arms: Faecal parasite egg counts on sub-set of children (n =120, split approximately equal across treatment arms) Urine samples

Procedures: End of trial	Ultrasonography - WHO Niamey Protocol Faecal parasite egg counts Blood sample Urine sample Final treatment
Procedures for safety mon- itoring during trial	Treatment observed and managed for AEs for at least one hour after administration. 24-hour post-treatment follow-up of participants by health professional. Treatment side effects recorded. Severe adverse effects reported to [name], VCD-Ministry of Health and [name], University of Cambridge ([name], University of Cambridge, CI maternity cover) for notifications
Criteria for withdrawal of participants	Severe Adverse Event/Reaction Withdrawal of assent/consent

5. Trial Flow Chart

Final outcome measured 2-years post 1^{st} treatment. Intermediate assessments at 1-year post 1^{st} treatment.

Assessment for primary outcomes – Ultrasonography according to WHO Niamey Protocol for Schistosomiasis. Prevalence of periportal fibrosis (protocol scores C, D, E or F) at 2-years.

Assessment for secondary and exploratory outcomes :-

Stool sample collection for parasitology egg counts, pre-annual treatment and around 4-weeks post treatment at baseline and 2-years for treatment efficacy measurement.

Blood sample collection for monitoring of host immuno-pathological responses.

6. Introduction

6.1. Background

Periportal fibrosis is the severest pathology caused by schistosomiasis mansoni. Large fibrotic deposits in the liver can lead to portal hypertension, and death by haematemesis (1). The cornerstone of disease control is annual preventative chemotherapy (PC) through mass administration (MDA) of the safe and efficacious drug praziquantel (PZQ).

Page 13 of 48

Elimination of schistosomiasis as a public health problem is promoted as global health priority in the WHO Roadmap to Neglected Tropical Disease (NTD) Control. The Roadmap stipulates annual treatment with praziquantel of 75% of all school-aged children living in schistosome endemic areas by the year 2020. This is the age-group that carries the greatest burden of infection. Community treatment is recommended in areas of intense transmission (2). The WHO roadmap has been strengthened by World Health Assembly Resolution 65.21. The resolution calls for a concerted effort to achieve the target of 75% treatment coverage, and a highly ambitious target of moving towards elimination of infection where possible.

Working with the Schistosome Control Initiative, Uganda was one of the first countries to introduce MDA of PZO, with the first communities receiving treatment in 2003 located on the shores of Lake Albert (3). The inhabitants of these fishing communities had very high infection intensities, and a record in the 20th century scientific literature of highly prevalent severe schistosomiasis (4–6). Responding to more recent reports in this area of high numbers of individuals attending health clinics with end-stage schistosomiasis, we recently conducted a parasitological and ultrasound screen in these fishing communities and found periportal fibrosis to be commonplace. Worryingly fibrotic patterns are not restricted to those of the older generation, ruling out the scenario that the fibrosis is present due to childhood exposure amongst those too old to have received treatment through MDA when they were school-aged. Amongst the 910 school-aged children (aged 7-15yrs) examined in Hoima District, 82% were found to have ultrasound detectable periportal fibrosis and 31% had central fibrosis, the manifestation most likely to lead to increases in portal pressure. The longstanding current intervention strategy is therefore not preventing morbidity in this region, with an unacceptably high percentage of children presenting with severe periportal fibrosis, and those children with mild periportal fibrosis being at risk of progression towards more severe disease. Highlighting this is the finding that amongst the adults screened, 56% had central periportal fibrosis, 24% with grades considered very severe and likely to respond poorly to treatment with PZQ. This is despite concerted efforts to treat annually, with the latest reported community MDA coverage rates for the district being 81%.

Large-scale cluster intervention trials on optimal treatment have been implemented by the Schistosomiasis Consortium for Operational Research and Evaluation (SCORE), their design focusing on annual treatment, comparing either a community or school-based approach, with treatment holidays (to free resources for other public heath activities) (7). Spatial analysis of the Kenyan SCORE trial shows annual interventions failing to decrease infection intensity in transmission hotspots over the 5-years of the trial (8). A similar result of persistent hotspots was also found in the Tanzanian SCORE trial. Here hotspots were found to be independent of treatment coverage, and likely caused by an underlying high intensity of transmission and a consequent high force of infection (9). As periportal fibrosis is a focal manifestation due to transmission patterns and underlying host-parasite interactions, other areas where annual treatment fails to control infection levels, and are hotspots of morbidity such as Hoima

ISRCTN Number: 16994599 Page 14 of 48

District, are likely to exist. While undoubtedly annual MDA has been a major public health advancement, the current strategies are falling short of the goal of Sustainable Development Goal 3, which promotes good health for all and indeed of the specific control targets for schistosomiasis articulated by the WHO.

6.2. Clinical Data

Praziquantel – tablet, ~40mg/kg according to WHO dose pole (10), maximum of 5 tablets. Registered for children aged 4-years or more. Listed on WHO Model List of Essential Medicines.

6.2.1. Efficacy

A tentative threshold of 90% egg reduction rate has been set by WHO as an indicator of optimal efficacy.

6.2.2. Safety and tolerability

Praziquantel: side-effects increase with dose and duration of treatment with the more severe reactions being associated with longer and heavier doses that are required for non-schistosome platyhelminth infections e.g. neurocysticercosis (50mg/kg/day for 15 days).

```
Neurological
```

Headaches – very common (>10%)

Dizziness – very common (>10%)

Vertigo, drowsiness - common (1-10%)

Seizures – very rare (<0.01%)

Gastro-intestinal

Gastrointestinal and abdominal pains - very common (>10%)

Nausea – very common (>10%)

Vomiting – very common (>10%)

Anorexia – common (1 – 10%)

Diarrhoea – common (1 – 10%)

Bloody diarrhoea - very rare (<0.01%)

Dermatological

Urticaria - very common (>10%)

Cardiovascular

Unspecified arrhythmias – very rare (<0.01%)

Immune system disorders

Allergic reaction – very rare (<0.01%)

Polyserositis – very rare (<0.01%)

Eosinophilia – very rare (<0.01%)

Jarisch-Herxheimer reaction - very rare (<0.01%)

Hepatobiliary disorders

Liver function tests increased - rare (0.01 - 0.1 %)

Musculoskeletal and connective tissue disorders

Myalgia – common (1 – 10%)

ISRCTN Number: 16994599 Page 15 of 48

General disorders
Fatigue-very common (>10%)
Feeling unwell (asthenia, malaise) – common (1 – 10%)
Fever- common (1 – 10%)

Adverse reactions with food, over the counter drugs or commonly prescribed drugs are not reported.

6.2.1. Pharmacokinetics & pharmacodynamics

Half-life (serum) 0.8-1.5 hours. Extensive first-pass effect for metabolism. Renal metabolism. Excretion 80% within 4-days, mostly within urine.

7. Rationale for Trial

An alternative to the standard annual treatment for areas of high persistent morbidity is desperately required if the target of good health for all and schistosomiasis control is to be met. Integrated approaches of MDA, WASH (water, sanitation and hygiene) (11) and where appropriate, intermediate snail host control (12), are proposed long-term strategies to drive down transmission in hot-spots. However, where persistent morbidity occurs, disease control strategies that will have a more immediate effect are required to prevent further generations progressing to severe, difficult-to-treat schistosomiasis with potentially irreversible sequelae.

Although a range of morbidity indicators are included as outcomes of ongoing trials, there exist no published controlled intervention trials specifically examining the effect of treatment frequency on ultrasound detectable periportal fibrosis in high morbidity areas; the SCORE Gaining Control studies are being conducted in Lake Victoria transmission areas where the prevalence of school-aged periportal fibrosis is very low (<1%) (13). This low prevalence is in agreement with previous observation studies on Lake Victoria (14). The published literature on the resolution/regression of periportal fibrosis with treatment solely covers single intervention strategies, mostly annual (15-19) but also biannual treatment (20). They examine different aged cohorts and have varying follow-up periods, stretching from 7-months (15) to three years (16,19,21) and show clear geographical differences that will represent both transmission and host-parasite interaction dynamics. This previous literature indicates that regression of central fibrosis occurs at a faster rate than complete resolution of fibrosis, the former being detectable by 7-months in school-aged children (15), and the latter at 2-years (17). None achieve 100% disease resolution, with some individuals within the cohorts showing progression in severity of morbidity under the interventions.

Autopsy studies have shown conclusively that periportal fibrosis is solely attributable to schistosomiasis and is associated with high worm burdens (1). With the introduction of portal ultrasound machines, community studies have shown, however, that the highest *S. mansoni* infection intensities are not always significantly associated with periportal fibrosis: infection intensities peak in adolescence and the prevalence of fibrosis peaks in adulthood (22). Severe periportal fibrosis therefore seems to result from cumulative exposure to high infection intensities throughout childhood, and if

untreated increasing in severity towards adulthood (6). Correspondingly, when community-based PZQ treatment interventions are paired with monitoring of disease regression, periportal fibrosis is found to resolve more readily both in younger members of cohorts and those with milder fibrosis scores (16,18,23).

While in our Hoima District screen there is no significant increase in infection intensities between children without fibrosis and those with peripheral fibrosis (fibrosis of the segmental branches of the portal vein, but no fibrosis around the central portal vein), the PZQ intervention literature supports the resolution of this milder form of periportal fibrosis through chemotherapeutic intervention (16,20). In addition, in agreement with studies of school-aged children (23), a clear association between increased infection intensities and presentation with central fibrosis and worsening of this central fibrosis was observed. By implication, if we can drive down the infection burden amongst children, the prevalence of central fibrosis, that most likely to cause the severe manifestation of PHT, should also decrease. The link between infection intensity and the severest patterns suggests that resolution, even in this small subset of children may be achievable, contrary to the evidence linking severity of periportal fibrosis to poor resolution in adulthood (20).

Increasing PZQ dosage to 60mg/kg results in no significant difference in egg reduction rate (24,25), and 2 doses 2 weeks apart, although increasing cure rate, fails to have a long-term effect on infection intensities (26). Alternative annual treatment regimens therefore are unlikely to provide valid solutions. However, while not directly relating *S. mansoni* infection intensities to morbidity, increased PZQ treatment frequency is successful at reducing the infection burden amongst school children (27). Where periportal fibrosis is found to still occur, targeting increased frequency of intervention at school-aged children is likely to be a successful strategy to resolve much of the periportal fibrosis observed and prevent disease progression for others amongst these younger generations. However, this change in treatment regime requires evaluation, including validation of the required frequency of treatment, prior to recommendation for implementation.

Aim: To evaluate whether increasing treatment frequency with praziquantel through school- based /school-community based delivery strategies reduces the prevalence of childhood periportal fibrosis in schistosomiasis morbidity hot-spots after two years of intervention.

8. Trial Design

8.1. Statement of Design

This is a phase IV, randomised superiority trial that is blinded to the primary outcome assessors, but open label to all other investigators and participants.

8.2. Number of Centres

1

8.3. Number of Participants

We plan to include 600 participants in this trial. Given the disruption caused by the COVID-19 pandemic to the communities from which the participants for this trial are identified, we anticipate this may require up to 750 participants to be enrolled; however we will continue to recruit participants until target participant completion is achieved.

8.4. Participants Trial Duration

Participants will be enrolled prior to the start of any other trial visits/treatments. The active treatment phase will last 2-years. All participants will be enrolled for the duration of the 2-year follow-up post 1st treatment. The time the participants will be enrolled in the trial has been elongated due to COVID-19 restrictions. Please see Diagram 'Chronological Trial Plan' in Section 12.6

8.5. Trial Objectives

8.5.1. Primary objective

To compare the effect of 2x and 4x treatments annually with praziquantel to the standard 1x annual treatment on the prevalence of *Schistosoma mansoni* associated periportal fibrosis of the liver.

8.5.2. Secondary objective

To compare the effect of 2x and 4x treatments annually with praziquantel to the standard 1x annual treatment on the mean infection intensity of *Schistosoma mansoni*.

8.6. Trial Outcome Measures

8.6.1. Primary outcome measure

The primary outcome is prevalence of periportal fibrosis, defined as Niamey Protocol pattern scores of C, D, E or F, measured at 2-years post 1st treatment follow-up.

8.6.2. Secondary outcome measure

The secondary outcome is *Schistosoma mansoni* infection intensities as measured by Kato-Katz faecal egg counts (28), measured at 2-years post 1st treatment follow-up.

8.6.3. Exploratory outcome measure

An exploratory secondary use of the trial data will be mathematical modelling of predicted long-term success of trial strategy. One year interim assessments of infection levels are to be taken to improve the fit of these models.

An exploratory outcome measure is the *S. mansoni* egg reduction rate, measured post treatment at baseline + 4 weeks and 2-years + 4 weeks, with accompanying parasite genetic/genomic characterisation. Processing of stool samples for parasite isolation will solely be conducted on samples received from participants who tested positive for *S. mansoni* infection using a point-of-care urinary dipstick that detects circulating cathodic antigen (CCA).

An exploratory outcome measure is host immuno-pathological responses to the eggs of the parasite. This will be measured at baseline, and if local conditions permit at the 2-year follow-up.

9. Community, School and Trial Team COVID-19 precautions

All Trial activities carried out by the trial team members will be performed following the COVID-19 precaution national guidelines and the trial Risk Mitigation Plan for the duration of the pandemic in Uganda. Any future national guidelines issued by the Ugandan Government will be reviewed by the Sponsor alongside the trial Risk Mitigation Plan and implemented as required.

ISRCTN Number: 16994599

10. Selection and withdrawal of participants

10.1. Inclusion Criteria

To be included in the trial the participant must:

- Have a parent/guardian who has given written/marked informed consent for the child to participate
- Have given written/marked informed assent to participate
- Be aged 6-14-years of age.
- Be born or resident within the community in which their school is situated for >=2 years.

10.2. Exclusion Criteria

The presence of any of the following will preclude participant inclusion:

- History of facial oedema after treatment with praziquantel
- Known neurocysticercosis or intraocular cysticercosis

10.3. Treatment Assignment and Randomisation Number

Prior to enrolment trial participant identification numbers will be generated and these numbers assigned an intervention arm via simple computer generated random number randomisation. This paper-based list will be provided to the trial site team and upon enrolment children will be assigned to the ordered participant identification numbers, class-by- class and school-by-school or household or household if schools are not open and school-by-school. Randomisation will be stratified by school.

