10.4. Method of Blinding

Open label to participants and the investigators, with the exception of the ultrasonographers who are undertaking the scoring for the primary trial outcome. Scoring will be undertaken remotely from the participant being examined, via a video link of the structured ultrasound examination, without audio, and the technicians who are undertaking the egg counts for the secondary outcome.

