17.2. Number of Participants to be enrolled

Berhe et al 2008 (20) reported a 47.7% resolution rate of grade C to non-periportal fibrosis scores of A and B and 24.6% resolution rates of D scores to scores A and B. Extrapolating this success rate onto our preliminary data, we would expect 35% less of the children in a successful intervention arm to have periportal fibrosis after 2-years intervention than those in the control arm. However, Berhe et al also reported geographical differences in resolution, with higher transmission villages having poorer resolution. We therefore propose a minimum 20% absolute difference in prevalence of periportal fibrosis between the control and intervention arms to be a clinically significant outcome. Based on preliminary data we assume an incidence rate of scores C-F of 80% in the control arm. With a Bonferroni correction to allow any pairwise comparison between the three arms, testing at a 1.66% significance level, a total sample size of 450, 150 per arm, would provide 92% power to detect an absolute reduction of 20%. In previous Lake Victoria fishing community observation studies, failure to follow-up has been as high as 35%. The communities on Lake Albert are more stable ([name], pers. comm.) but to minimise failure to follow-up, selection is restricted to children in P1 to P4, retaining the cohort within the primary school structure over the two years of the study, and an inclusion criteria of born or resident in the village for >2yrs, displaying stability of their household within the village is included. A failure to follow-up of 25% is included in the final study numbers. Six hundred primary school-aged children will be enrolled into the study, with 200 randomised into each of the three intervention arms. Given the disruption caused by the COVID-19 pandemic to the communities from which the participants for this trial are identified, we anticipate this may require up to 750 participants to be enrolled to obtain the sample size of 600; however we will continue to recruit participants until target participant completion is achieved.

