26.1. Appendix 1 - Trial Management / Responsibilities

26.1.1. Participant registration/ Randomisation procedure

Receive parent/guardian consent for participation, and conduct the assent process within the school or village community environment. Eligible children will then be assigned class-by-class and school-by-school or household-by-household if the schools are not open and school-by-school to listed identification numbers. These identification numbers will have previously been assigned to an intervention arm. Randomisation will be stratified by school.

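### The open-label site team holds a paper list of IDs already tied to arms, with no concealment described, and the method is called both simple and stratified by school without blocks

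*Protocol*

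**What the plan says.** Three statements in section 10.3 fix the allocation procedure.

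- Timing and method: "Prior to enrolment trial participant identification numbers will be generated and these numbers assigned an intervention arm via simple computer generated random number randomisation".
- Who holds the list: "This paper-based list will be provided to the trial site team and upon enrolment children will be assigned to the ordered participant identification numbers". Children are placed on it taking classes and schools in turn, or households if schools are closed.
- Stratification: "Randomisation will be stratified by school".

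Section 26.1.1 (Appendix 1) puts parental consent and child assent first. Then: "Eligible children will then be assigned class-by-class and school-by-school". It adds: "These identification numbers will have previously been assigned to an intervention arm". It repeats that randomisation is stratified by school.

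Section 10.4 on blinding reads: "Open label to participants and the investigators, with the exception of the ultrasonographers". It also excepts the technicians who count eggs. Section 12.3.3 gives a 1:1:1 ratio. Section 17.2 plans 600 children, "with 200 randomised into each of the three intervention arms". Section 17.1 adjusts the primary analysis for school, baseline fibrosis score and egg count.

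**The concern.** Random allocation protects against selection bias only if the person who enrols a child cannot know the arm that child will receive. Here the sequence is fixed in advance, is on paper, runs in ID order and is with a team that is not blinded. Nothing in the text keeps the arm codes from the person who matches children to IDs.

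If that person knows the next arm, they can change who is approached, the order in which children come forward, or which class or household is visited next. Blinded reading of the ultrasound protects the measurement, not the make-up of the arms. Differences in features that nobody records, such as household stability or likely adherence, would carry into all three pairwise comparisons. Household stability is relevant because section 17.2 plans for 25% loss to follow-up.

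The second, lesser matter is that the method has two descriptions that do not fit together, and neither delivers the balance that the protocol implies.

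**Working it through.** **Concealment: the sections side by side**

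| Question | Section | Answer in the text |
|---|---|---|
| When is the arm fixed? | 10.3, 26.1.1 | Before enrolment, attached to the ID |
| Who has the list at enrolment? | 10.3 | The site team, on paper |
| In what order are IDs used? | 10.3 | In list order |
| Is the site team blinded? | 10.4 | No, apart from ultrasound scorers and egg-count technicians |
| Does consent come before the ID? | 26.1.1 | Yes |
| Masked arm column, envelopes, third-party or central release? | 10.3, 12.3.3, 26.1.1 | None described |

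In 10.3 the list handed over is, on its plain reading, the list of IDs just assigned to arms. Under simple randomisation past allocations do not reveal the next one, so possession of the list is what makes the next arm foreseeable. Withholding the arm codes would close that route.

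**Balance: the plan's own figure first**

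Inputs from 17.1 and 17.2: 80% against 60%, 150 per arm, two-sided 1.66%, 25% loss.

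- z for a two-sided 1.66% test = 2.395.
- Standard error under the null = √(2 × 0.70 × 0.30 / 150) = 0.0529.
- Standard error under the alternative = √((0.80 × 0.20 + 0.60 × 0.40) / 150) = 0.0516.
- Power = Φ((0.20 − 2.395 × 0.0529) / 0.0516) = Φ(1.42) ≈ 0.922. The stated 92% is reproduced.
- Enrolment = 450 / (1 − 0.25) = 600. Reproduced.

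**What simple 1:1:1 randomisation of 600 gives**

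- Mean arm size = 600 / 3 = 200.
- Standard deviation = √(600 × 1/3 × 2/3) = 11.5.
- 95% range for one arm, from 200,000 simulated allocations: about 178 to 223.
- Gap between largest and smallest arm: median 22, 95th percentile 47.

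**Within school.** The protocol does not give school sizes, so these are assumptions. In a school of 300 the gap has median 16 and 95th percentile 33. In a school of 150 it has median 11 and 95th percentile 23. Running separate simple lists per school would be stratified in name but would give no tighter balance, because nothing restricts the sequence.

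**Effect on power.** With 75% of each arm retained, pairwise power over the simulated arm sizes has mean 92.1% and a 95% range of about 90.3% to 93.6%.

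**The case against.** The strongest reply is that foreknowledge is inferred. A reader might conclude that allocation is shown to be unconcealed. The documents do not go that far: 10.3 does not say that the enroller sees the arm column or who in the team holds the list, and the wording of 26.1.1 could fit an ID-only sheet at the point of enrolment. This stands. The supportable statement is that no concealment is described and that the procedure as written allows foreknowledge.

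The protocol also has real safeguards. Consent and assent precede ID assignment, IDs are used in order, classes are taken in turn, outcome scoring is blinded, and 17.1 adjusts for school, baseline score and egg count. These narrow the room for steering. They do not hide the next arm, and adjustment cannot reach unmeasured features.

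A reader might try to size the bias by supposing that staff steer pattern D children rather than pattern C children into one arm and applying the resolution rates in 17.2. The documents do not support that. Sections 8.4 and 12.3.3 place enrolment before other trial visits, so staff would not yet have a trial ultrasound score to steer on. Section 12.1 mentions earlier screening data only for choosing schools. An imbalance in baseline score is also largely what the primary analysis adjusts for. Nor is the direction known: sending sicker children to the most frequent treatment would work against that arm.

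On arm sizes, 200 per arm is a planning number. Missing an exact 200/200/200 split is ordinary without blocking and is no measure of harm. That also stands.

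Finally, much of the allocation may be over. The amendment history for version 4 records that 26.1.1 was revised to match what took place. A new list would then help only later recruits, although 8.3 and 17.2 leave recruitment open.

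**Conclusion.** The concern holds in two parts of unequal weight.

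The main part is concealment. Sections 10.3 and 26.1.1 set out a procedure that allows the enroller to foresee the next arm, and the safeguards reduce this without removing it. This is not detail that can be left to a statistical analysis plan, because the protocol itself states the allocation procedure. No bias in points of prevalence can be derived from the documents, and none is claimed. The conclusion assumes that the list in 10.3 carries the arms, which is the plain reading but is not stated outright.

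The lesser part is the description. *Simple* and *stratified by school* need reconciling, and with no blocks neither balance within school nor 200 per arm is secured (about 178 to 223 for one arm of 600). This is a matter of balance and accurate reporting. The power loss is negligible, and adjustment for school limits the effect on the estimate.

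**What to change.** **For any further enrolment**, amend 10.3 and 26.1.1 as follows:

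- The trials unit generates the list and keeps the arm codes; the site list carries IDs only.
- The arm is released after consent and once the ID is irrevocably assigned, ideally after baseline scoring.
- The sequence is restricted within school, for example by permuted blocks. Block size should vary, because in an open-label trial past allocations are known.

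**For children already allocated:**

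- State the method actually used (simple, or restricted within school), who held the arm codes and when the arm became known.
- Check IDs against the enrolment log for unbroken sequence.
- Compare baseline characteristics by arm.
- If out-of-sequence allocations are found, add a sensitivity analysis that excludes them. This is a check, not a cure.

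The cost is revised wording, a centrally held list or sealed release for later recruits, and an audit of the existing log. No extra participants are needed.
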